a Participants who prematurely discontinue the study intervention (prior to completing the 24-week treatment period) should attend an Early Treatment Discontinuation (ETD) visit at earliest convenience with all the assessments planned for the End of Treatment visit (V5), except HRCT scans and IMP. In particular cases when the ETD visit is closed to a regular study visit, ETD could be merged and will replace the regular visit. In addition, the participants will be asked and encouraged to complete all the remaining study visits according to the visit schedule until and including the EOT visit (V5). Under exceptional circumstances when a participant cannot come to the site for the scheduled visit, a phone contact can be made after sponsor approval is given. During the phone contact, at least information about AEs and concomitant medication should be collected.

b Participants who prematurely discontinue the study should attend an Early Study Discontinuation (ESD) visit at earliest convenience with all the procedures planned for the End of Treatment Visit (Visit 5) except IMP. If the investigator considers that the time from the last HRCT scan exposure is not acceptable, the investigation will not be done.

c Post-treatment Follow-up: up to 12 Weeks or until the participants switch to commercialized dupilumab (or other biologic products), the call visit should be done first.

d Visit 6 will be a telephone visit. For the participants who switch to commercialized dupilumab (or other biologic products), the call visit should be done prior to the first injection with commercialized dupilumab (or other biologic products).

e Vital signs, including blood pressure (mmHg), heart rate (beats per minute), respiratory rate (breaths per minute), body temperature (degrees Celsius).

f A complete physical examination will include, at a minimum, assessments of the cardiovascular, respiratory, gastrointestinal and neurological systems and will be performed at V1, V2 and V5. Body weight (kg) will be measured at V1, V2 and V5. Height (cm) will be measured only at V1.

g Reversibility test: Three attempts may be performed during the screening period to meet the qualifying criteria for reversibility before randomization. This is only required if a reversibility test meeting eligibility criterion was not performed within 6 months prior to Visit 1.

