4 STUDY DESIGN

4.1 OVERALL DESIGN

This is a Phase 4 randomized, multinational study with a 24-week double-blind placebo-controlled period to explore the effect of dupilumab on airway inflammation through assessments of biomarkers, mucus plugging, and other lung imaging parameters in participants with asthma.

Study participation for each participant will be a total of minimum 29 weeks and up to 41 weeks.

The study includes 3 study periods:

- Screening period: 4 weeks (± 1 week), from signed informed consent to randomization.
- Randomized, placebo-controlled treatment period: 24 weeks from baseline (Day 1).
- Post treatment follow-up period: up to 12 weeks or until the participants switch to commercialized dupilumab (or other biologic products), whatever comes first.

Participants who fulfill the inclusion criteria and do not meet any of the exclusion criteria will be randomized (2:1) to one of the following investigational medicinal products (IMP).

- Dupilumab: participants will receive a loading dose of 600 mg of dupilumab (2 x 300 mg dupilumab SC on Day 1, followed by 300 mg every 2 weeks (Q2W) for 24 weeks.
- Placebo: participants will receive 2 x 2 mL placebo injections SC on Day 1, then 1 placebo injection Q2W for 24 weeks.

Randomization will be stratified by ICS dose level (medium/high- no less than 40% in 'high ICS' stratum) and region (Eastern Europe/ROW). In total, no more than 40% participants should be in "Eastern Europe" strata.

Study intervention discontinuation follow-up

Participants who prematurely discontinue the study intervention (prior to completing the 24-week treatment period) should attend an Early Treatment Discontinuation (ETD) visit at the earliest convenience with all the assessments planned for the End of Treatment (EOT) visit (V5), except HRCT and IMP. In particular cases when the ETD visit is close to a regular study visit, ETD could be merged and will replace the regular visit (See [Section 7.1.1](#)).

In addition, the participants will be asked and encouraged to complete all the remaining study visits according to the visit schedule until and including the EOT visit (V5).

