4.4 END OF STUDY DEFINITION

A participant is considered to have completed the study if he/she has completed all phases of the study including the post treatment follow-up visit (V6).

The end of the study is defined as the date of the last visit of the last participant in the study.

For the participants who permanently discontinue the planned treatment, the recommended follow-up is described in [Section 4.1](#).

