5.1 INCLUSION CRITERIA

Participants are eligible to be included in the study only if all of the following criteria apply:

Age

I 01. 18 to 70 years of age inclusive with the diagnosis of asthma based on Global Strategy for Asthma Management and Prevention (GINA) 2019 ([1](#)) at the time of signing the informed consent.

Type of participant and disease characteristics

I 02. History of ≥ 1 exacerbation(s) in the previous year before V1.

Exacerbation is defined as deterioration of asthma that results in emergency treatment, hospitalization due to asthma, or treatment with systemic steroids.

I 03. Uncontrolled moderate-to-severe asthma (ACQ-5 ≥ 1.5) at V1 and V2, prior to randomization.

I 04. Pre-bronchodilator FEV₁ $\leq 80\%$ of predicted normal at V1 and V2, prior to randomization.

I 05. Exhibit bronchodilator reversibility ($\geq 12\%$ and 200 mL improvement in FEV₁ post SABA administration) during screening, prior to randomization.

I 06. Blood eosinophil ≥ 300 cells / μ L and FeNO ≥ 25 ppb during screening and prior to randomization.

NOTES:

- Historical values of blood eosinophil count meeting the eligibility criterion measured within 6 months prior to SV1 in the absence of OCS treatment are allowed.
- FeNO value to be checked for eligibility at V2 as well.

I 07. Existing treatment with medium to high dose ICS in combination with a second controller (eg, LABA, LTRA) \pm a third controller. The dose regimen should be stable ≥ 1 month prior V1 and during screening.

I 08. Willing and able to comply with all clinic visits and study related procedures.

Weight

Not applicable.

Sex

I 09. Male and Female

Contraceptive used by men or women should be consistent with local regulations regarding the methods of contraception for those participating in clinical studies.

Female participants of childbearing potential are eligible to participate if they agree to use a highly effective method of contraception consistently and correctly during the intervention period and up to 12 weeks after last dose of study intervention or until the participants switch to commercialized dupilumab (or other biologic products), whatever comes first, as described in [Section 10.4](#) (Appendix 4).

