7.2 PARTICIPANT DISCONTINUATION/WITHDRAWAL FROM THE STUDY

- A participant may withdraw from the study at any time at his/her own request or may be withdrawn at any time at the discretion of the Investigator for safety, behavioral, compliance, or administrative reasons. This is expected to be uncommon.
- Participants who prematurely discontinue the study, should attend an Early Study Discontinuation (ESD) visit at the earliest convenience with all the procedures planned for the End of Treatment Visit (Visit 5) except IMP, as shown in the SoA ([Section 1.3](#)). See SoA for data to be collected at the time of study discontinuation and follow-up and for any further evaluations that need to be completed. If the Investigator considers that the time from the last HRCT scan exposure is not acceptable, the investigation will not be done.
- The participant will be permanently discontinued both from the study intervention and from the study at that time.
- If the participant withdraws consent for disclosure of future information, the Sponsor may retain and continue to use any data collected before such a withdrawal of consent.
- If a participant withdraws from the study, he/she may request destruction of any samples taken and not tested, and the Investigator must document this in the site study records.

If participants no longer wish to take the IMP, they will be encouraged to remain in the study.

The investigators should discuss with them key visits to attend. The value of all their study data collected during their continued involvement will be emphasized as important to the public health value of the study.

Participants who withdraw from the study intervention should be explicitly asked about the contribution of possible AEs to their decision, and any adverse event (AE) information elicited must be documented.

All study withdrawals should be recorded by the Investigator in the appropriate screens of the e-CRF and in the participant's medical records. In the medical record, at least the date of the withdrawal and the reason should be documented.

In addition, a participant may withdraw his/her consent to stop participating in the study. Withdrawal of consent for intervention should be distinguished from withdrawal of consent for follow-up visits and from withdrawal of consent for non-participant contact follow-up, eg, medical record checks. The site should document any case of withdrawal of consent.

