8.3.1 Time period and frequency for collecting AE and SAE information

All SAEs will be collected from the signing of the ICF until the follow-up visit at the time points specified in the SoA ([Section 1.3](#)).

All AE will be collected from the signing of the ICF at the time points specified in the SoA ([Section 1.3](#)).

All SAEs and AESI will be recorded and reported to the Sponsor or designee immediately and under no circumstance should this exceed 24 hours, as indicated in Appendix 3 ([Section 10.3](#)). The Investigator will submit any updated SAE data to the Sponsor within 24 hours of it being available.

Investigators are not obligated to actively seek AE or SAE after conclusion of the study participation. However, if the Investigator learns of any SAE, including a death, at any time after a participant has been discharged from the study, and he/she considers the event to be reasonably related to the study intervention or study participation, the Investigator must promptly notify the Sponsor.

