9.4.2 Safety analyses

All safety analyses will be performed on the safety population and will be presented by treatment group.

The treatment-emergent is defined as the period of time from the date and time of the first dose of IMP through the date of last dose + 12 weeks (or the day before switch to commercialized dupilumab or other biologic treatment, whichever occurs first).

Table 8 - Safety analyses

Endpoint	Statistical Analysis Methods
Secondary	
 Incidence of TEAEs, TESAEs, TEAE leading to study intervention discontinuation and AESI Adverse event incidence tables will be presented by system organ class (SOC) (sorted by internationally agreed order), high-level group term (HLGT), high level term (HLT) and preferred term (PT), the number (n) and percentage (%) of participants experiencing an AE. Multiple occurrences of the same event in the same participant will be counted only once in the tables. The denominator for computation of percentages is the safety population within each treatment group. Proportion of participants with at least one TEAE, serious TEAE, AESI, and TEAE leading to discontinuation of the study intervention will be tabulated by treatment group. In addition, TEAEs will be described according to maximum intensity and relation to the study drug. Serious AEs and AEs leading to study discontinuation that occur outside the treatment-emergent period will be summarized separately.

Multiplicity Considerations for the secondary endpoints

A multiplicity control procedure and the selected list of secondary endpoints to be tested in the hierarchical order will be specified in the Statistical Analysis Plan. Regardless of eligibility to be declared significant, results for all comparisons will be presented. Descriptive statistics including number of participants, mean, standard deviation, and LS means will also be provided.

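### Instructions for early treatment stoppers end at V5, so a last dose after Week 12 may not be observed for the protocol's 12-week treatment-emergent period

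*Protocol*

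**What the plan says.** For a participant who stops treatment before Week 24, protocol Section 4.1 calls for an early treatment discontinuation visit and then asks and encourages the participant to "complete all the remaining study visits according to the visit schedule until and including the EOT visit (V5". Section 1.3 footnote a and Section 7.1.1 give the same end point, and SAP Section 15.2 repeats the footnote. Section 4.4 counts the V6 follow-up visit as part of completing the study, but then adds "For the participants who permanently discontinue the planned treatment, the recommended follow-up is described in" Section 4.1.

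For a participant who leaves the study, footnote b and Section 7.2 provide one Early Study Discontinuation (ESD) visit, after which "The participant will be permanently discontinued both from the study intervention and from the study at that time".

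Other sections look further ahead:

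- Section 9.4.2 runs the treatment-emergent period "through the date of last dose + 12 weeks (or the day before switch to commercialized dupilumab or other biologic treatment", whichever is first.
- Inclusion criterion I 09 requires contraception "during the intervention period and up to 12 weeks after last dose of study intervention", or until the switch.
- Section 8.3.1 states that "All SAEs will be collected from the signing of the ICF until the follow-up visit".
- Section 7.1.1 keeps treatment stoppers in the study for safety as well as efficacy.
- V6 is a telephone visit with AE review and a home pregnancy test (Section 1.3).

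**The concern.** The sections that tell a site what to do with an early stopper end at Week 24, counted from Day 1. The section that defines which events count runs from the last dose. These are different clocks, and for a late stopper the first runs out before the second.

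A site that follows the specific instruction would not schedule the V6 call, so new adverse events in the rest of the 12 weeks would reach the database only if the participant volunteered them. Section 8.3.1 also says that investigators need not actively seek events once participation has ended. The incidence tables divide by the whole safety population in each arm (protocol Section 9.4.2, SAP Section 9.1), and none of the planned summaries shows how long each person was observed after the last dose. Safety incidence is a stated secondary endpoint.

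**Working it through.** **Inputs.** V5 falls at Week 24, target study day 169 (SAP Table 15-2). Dosing is every 2 weeks from Day 1 (protocol Section 6.1). The treatment-emergent period is last dose plus 84 days (Section 9.4.2). Screening is 4 weeks ± 1, treatment 24 weeks, and follow-up up to 12 weeks (Section 4.1).

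**The plan's own figures.** Participation: 5 + 24 + 0 = 29 weeks and 5 + 24 + 12 = 41 weeks, as stated. Sample size: 87 / 0.90 = 96.7, rounded up to 97, as stated.

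**Completers.** The schedule places V6 at up to Week 36. A last dose at Week 24 gives 36 − 24 = 12 weeks, and a last dose at Week 22 gives 36 − 22 = 14 weeks. The window can be reached when V6 takes place at Week 36.

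**Early stoppers followed to V5.** For a last dose at week L, given on day 1 + 7L, observation at V5 is 169 − (1 + 7L) days, which is 24 − L weeks. The shortfall is max(0, L − 12) weeks.

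| Week of last dose | Weeks observed at V5 | Weeks short of 12 |
|---|---|---|
| 0 to 12 | 24 to 12 | 0 |
| 14 | 10 | 2 |
| 16 | 8 | 4 |
| 18 | 6 | 6 |
| 20 | 4 | 8 |
| 22 (if premature) | 2 | 10 |

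Week 22 is a premature stop only if a Week 24 dose is scheduled. Footnote a suggests one, because it excepts IMP from the V5 assessments. The window is covered for 7 of 11 possible premature last-dose times if the last scheduled dose is Week 22, and for 7 of 12 if it is Week 24. These are counts of dosing times, not of people.

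**Sensitivity to the visit window.** With V5 three days early (day 166), a last dose at Week 12 gives 166 − 85 = 81 days, 3 short of 84. The cut-off then moves to Week 10.

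**Study leavers.** The documents give no timing for the ESD visit beyond the earliest convenient date. If it falls 0 to 4 weeks after the last dose (an assumption), 12 to 8 of the 12 weeks are unobserved.

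**SAP window.** SAP Section 9 uses 98 days after last dose, up to the end of follow-up. On that count, full coverage at V5 needs a last dose at Week 10 or earlier. The 84-day and 98-day definitions are a separate inconsistency that also needs reconciling.

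**The case against.** The strongest reply is that V6 is never expressly withdrawn. Section 4.1 lists the follow-up period without excluding stoppers. Section 7.1.1 keeps them in the study for safety and says they are followed according to the schedule of activities, which contains V6. Section 8.3.1 makes no exception for them. This stands in part: a reader might infer that the protocol deliberately drops V6 for stoppers, and the text is ambiguous rather than exclusionary. But the schedule's own footnote for this group stops at V5, and Section 4.4 sends the reader to Section 4.1, which does the same. The specific instruction is the one a site is likely to follow.

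Second, much of what matters is already collected. Investigators remain responsible for following AEs that are serious, related or led to stopping (Section 8.3). SAEs and AESIs are followed to resolution or stabilization (Section 8.3.3), pregnancies to outcome (Section 8.3.5), and related SAEs learned of after discharge must be reported. This stands. A reader might infer that the events that caused people to stop are lost, and they are not. What is left is new events that nobody is scheduled to ask about.

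Third, 12 weeks is a ceiling for everyone, since follow-up may end at a switch to a biologic. That is true, but the protocol's treatment-emergent period closes at the switch too. It does not close at V5 for a stopper who has not switched.

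Fourth, Section 7.2 expects withdrawal from the study to be uncommon, and ending scheduled visits when someone leaves is ordinary. This also stands, and makes the ESD part of the point the weaker one.

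**Conclusion.** The passages conflict and should be reconciled. If V6 does not apply after early treatment discontinuation, a participant whose last dose is at Week 14 to 20 is observed for 10 down to 4 of the 12 weeks that the protocol counts (2 weeks for Week 22, if premature). Someone who leaves the study has no scheduled contact after the ESD visit. These figures assume on-schedule dosing and V5 on day 169. Attendance at V5 is only encouraged, so coverage of the earlier stoppers also depends on their coming.

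Four stronger readings are not supported:

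- That early stoppers in general go unobserved. Those with a last dose at Week 12 or earlier who attend V5 have the full window or more.
- That about 10 people are affected. 97 − 87 = 10 is the dropout allowance for evaluable participants. It does not count late treatment stoppers, a number the documents do not give.
- That the arm comparison is biased. Missed time can lower the counted incidence, but no difference in late stopping between the arms is stated or derivable.
- That specifically late reactions are missed. Section 2.3 names serum sickness and symptomatic eosinophilia as risks but does not describe them as arising after the last dose.

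The point is a modest weakness in safety ascertainment that is cheap to repair.

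**What to change.** In the protocol, reconcile Section 1.3 footnote a and Sections 4.1, 4.4 and 7.1.1 with Sections 9.4.2 and 8.3.1 and criterion I 09. State that the existing V6 telephone visit (AE review and home pregnancy test) also applies to every dosed participant who stops treatment early. Time it so that collection reaches the protocol's own 12 weeks after last dose, or the switch. In footnote b and Section 7.2, offer the same call to study leavers who still permit contact; Section 7.2 already separates the levels of consent withdrawal. Align the footnote in SAP Section 15.2.

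In the SAP, report time observed after last dose by arm beside the TEAE tables.

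The added follow-up beyond V5 is L − 12 weeks: 2, 4, 6 and 8 weeks for last doses at Weeks 14, 16, 18 and 20, and none for Week 12 or earlier when V5 is attended on schedule. The cost is protocol wording, one phone call for each late stopper, slightly more site work and one extra summary.

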4.2 SCIENTIFIC RATIONALE FOR STUDY DESIGN

A randomized, placebo-controlled study design where the effects of the IMP is assessed over the stable dose of maintenance therapy is considered to be the most appropriate design to investigate the objectives of this study. A randomization ratio of 2:1 for the active treatment versus placebo was incorporated into the study design in order to limit the number of participants exposed to placebo.

4.3 JUSTIFICATION FOR DOSE

The dose regimen of SC dupilumab selected for this study is 300 mg Q2W. Participants will receive an initial loading dose of 600 mg (2 x 300 mg) dupilumab on Day 1, and Q2W dosing will commence 2 weeks after the loading dose. The administration of the loading dose of dupilumab will allow systemic concentrations to reach target saturation, potentially reducing the time to onset of clinical effect.

Proof of concept has been established in the ACT11457 study (34) with 300 mg weekly dosing. One hundred and 4 participants with persistent, moderate-to-severe asthma and a blood eosinophil count of at least 300 cells/ μ L or a sputum eosinophil level of at least 3%, partially controlled or uncontrolled by medium-to-high doses of ICS plus long-acting β 2 agonists (LABA (fluticasone/salmeterol, budesonide/formoterol, or mometasone/formoterol) were randomized to the study. The study showed significant efficacy in a population of mostly severe asthmatics with poor asthma control and decreased lung function with mostly high doses of ICS in combination with a LABA.

The results from the Phase 2b dose ranging study (DRI12544) (35) showed that 300 mg Q2W and 200 mg Q2W treatment with dupilumab provided a significant improvement on FEV₁ at Week 12 and a statistically significant reduction in the annualized rate of severe exacerbations when compared to placebo. Both dose regimens provided comparable efficacy on most of the efficacy endpoints. Both doses were safe and well tolerated with a profile comparable to that seen with placebo except for an increased number of injection site reactions. To further characterize the optimal regimen for patients, both regimens were assessed in the Phase 3 study (QUEST) (22), which confirmed the findings from previous studies, showing comparable efficacy and safety profile in both 200 mg Q2W and 300 mg Q2W dose regimens, with an overall positive benefit-risk profile for dupilumab in comparison to placebo.

The focus of this study is to characterize the anti-inflammatory effect of dupilumab, which will be mainly evaluated using FRI analyses. In order to ensure maximum anti-inflammatory effect of dupilumab, the highest approved dose (300 mg) has been selected.

4.4 END OF STUDY DEFINITION

A participant is considered to have completed the study if he/she has completed all phases of the study including the post treatment follow-up visit (V6).

The end of the study is defined as the date of the last visit of the last participant in the study.

For the participants who permanently discontinue the planned treatment, the recommended follow-up is described in [Section 4.1](#).

